9.1.1 Solicited Events

The term “reactogenicity” refers to solicited signs and symptoms (“solicited events”) occurring in the hours and days following a vaccination. Participants will be assessed for reactogenicity, to be collected for 7 days following each vaccination (the day of vaccination and the following 6 days), using a paper diary (pDiary). Solicited events will be recorded in the eDiary for the periods Day 1 to Day 7 and Day 22 to Day 28.

Solicited administration site events

Solicited administration site events for this study are pain, redness, and swelling. Solicited administration site events will be recorded according to the vaccine that was administered most recently.

Solicited systemic events

Solicited systemic events for this study are fatigue, fever, nausea, vomiting, diarrhea, abdominal pain, headache, muscle ache, joint pain, shivering (chills), sweating. The preferred location for measuring temperature in this study is oral. Solicited events will be summarized according to the defined severity grading scales in Table 10. Fever will be considered as a body temperature value $\geq 38^{\circ}\text{C}$.

Table 10 Solicited Event Intensity Grades

Adults (≥ 18 years)		
Event	Intensity grade	Parameter
Pain at administration site	0	None
	1	Mild: Any pain neither interfering with nor preventing normal every day activities.
	2	Moderate: Painful when limb is moved and interferes with every day activities.
	3	Severe: Significant pain at rest. Prevents normal every day activities.
Headache	0	Normal
	1	Mild: Headache that is easily tolerated.
	2	Moderate: Headache that interferes with normal activity.
	3	Severe: Headache that prevents normal activity.
Fatigue	0	Normal
	1	Mild: Fatigue that is easily tolerated.
	2	Moderate: Fatigue that interferes with normal activity.
	3	Severe: Fatigue that prevents normal activity.
Muscle ache	0	Normal
	1	Mild: Muscle aches that are easily tolerated.
	2	Moderate: Muscle aches that interfere with normal activity.
	3	Severe: Muscle aches that prevent normal activity.
Joint pain	0	Normal
	1	Mild: Joint pain that is easily tolerated.
	2	Moderate: Joint pain that interferes with normal activity.
	3	Severe: Joint pain that prevents normal activity.
Shivering (chills)	0	Normal
	1	Mild: Shivering (chills) that is easily tolerated.
	2	Moderate: Shivering (chills) that interferes with normal activity.
	3	Severe: Shivering (chills) that prevents normal activity.
Sweating	0	Normal
	1	Mild: Sweating that is easily tolerated.
	2	Moderate: Sweating that interferes with normal activity.
	3	Severe: Sweating that prevents normal activity.
Gastrointestinal symptoms: nausea, vomiting, diarrhea and/or abdominal pain	0	Normal
	1	Mild: Gastrointestinal symptoms that are easily tolerated.
	2	Moderate: Gastrointestinal symptoms that interfere with normal activity.
	3	Severe: Gastrointestinal symptoms that prevent normal activity.
Redness at administration site	Record greatest surface diameter in mm	
Swelling at administration site	Record greatest surface diameter in mm	
Temperature*	Record temperature in °F	

* Refer to the Protocol Schedule of Assessments for the definition of fever and the preferred location for temperature measurement.

The maximum intensity of local injection site redness/swelling will be scored at GSK as follows:

0:	≤ 20 mm
1:	> 20 to 50 mm
2:	> 50 to 100 mm
3:	> 100 mm

The maximum intensity of fever will be scored at GSK as follows:

0:	< 38.0°C (< 100.4°F)
1:	≥ 38.0 – 38.4°C (≥100.4 – 101.2°F)
2:	≥ 38.5 – 38.9°C (≥ 101.3 – 102.1°F)
3:	≥ 39.0 – 40.0°C (≥ 102.2 – 104.0°F)
4:	> 40.0°C (>104.0°F)

1. Participants with solicited events will be counted based on actual intervention received for each study group and age group. Solicited events will also be presented by individual vaccine received (dose 1 and dose 2). The following categories will be included in the summary table for solicited events and will be generated on subjects who has filled in solicited symptom in the eDiary: Participants who experienced any solicited event within 7 days of vaccination
2. Participants who experienced any systemic solicited event within 7 days of vaccination
3. Participants who experienced any administration site solicited event within 7 days of vaccination

A summary table containing the number and percentage of participants showing the occurrence of any solicited event will be presented by study group, age group, visit, and timepoint. The duration of solicited events will also be summarized by study group, age group and vaccination.

The duration (in days) of a solicited event will be calculated as:

Date of last report of a solicited event after the respective vaccination administration date within 7 days of vaccination – date of first report of a solicited event after the respective vaccination administration date + 1

The duration (in days) of an ongoing solicited event after the 7 days of vaccination will be calculated as:

Date of last report of a solicited event after the respective vaccination administration date – date of first report of a solicited event after the respective vaccination administration date + 1

A similar calculation will be made for the second vaccination. Duration will be calculated for each solicited event separately.

A summary table for duration of solicited events within 7 days post-vaccination and a frequency table of solicited event after the 7 days of vaccination will be presented.

The number and percentage of participants experiencing each solicited event will be presented for each symptom maximal severity (defined in Table 10) by study group, age group, visit, and time point. If a solicited event occurs more than once for a participant within a time point, it will be counted in the summary only once, according to the maximal severity.

Solicited events will be listed.

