3. OBJECTIVES AND ENDPOINTS

Table 3 Study objectives and endpoints

[figure not shown]
Objectives	Endpoints
	Primary
Co-primary Immunogenicity: • To evaluate whether the monovalent influenza A/Hong Kong/125/2017-like (H7N9) virus vaccine containing 1.9 µg, 3.75 µg, or 7.5 µg of hemagglutinin (HA) adjuvanted with AS03 _A or AS03 _B elicits a hemagglutination inhibition (HI) antibody response to the vaccine-homologous virus that meets or exceeds the US Food and Drug Administration, Center for Biologics Evaluation and Research immunogenicity criteria at the Day 43 visit.	
 • Humoral immune response in terms of vaccine-homologous HI antibody titers: 
 – Seroprotection rates (SPR) at Day 43 – Seroconversion rates (SCR) at Day 43
Safety: • To describe the safety and reactogenicity of the different vaccine formulations through the Day 43 visit.	
 • Occurrence of adverse events (AEs) 
 – Solicited administration site events during a 7-day follow-up period (i.e. day of vaccination and 6 subsequent days) after each vaccination – Solicited systemic events during a 7-day follow-up (i.e. day of vaccination and 6 subsequent days) after each vaccination – Unsolicited AEs and medically attended adverse events (MAEs) for 21 days after each vaccination – Serious adverse events (SAEs), potential immune-mediated disease (pIMDs) up to Day 43 visit
Safety: • To describe the safety of the different vaccine formulations through Month 13	
 • Occurrence of pIMDs and SAEs until Month 13
	Secondary
• To describe the vaccine homologous H7N9 HI antibody profile in all study groups at Days 1, 22, and 43	
 • Vaccine-homologous (H7N9) HI antibody titers for each study group: 
 – Geometric Mean Titers (GMTs) at Days 1, 22, and 43 – Seropositivity rates at Days 1, 22 and 43 – SCR at Days 22 – SPR at Days 1 and 22 – Mean Geometric Increase (MGI) at Days 22 and 43
• To describe the vaccine homologous (H7N9) Microneutralization (MN) antibody profiles in a subset of participants at Days 1, 22, and 43	
 • Vaccine-homologous (H7N9) MN antibody titers for subset of participants: 
 – GMTs at Days 1, 22, and 43 – Seropositivity rates at Days 1, 22, and 43 – Vaccine response rate (VRR) at Days 22 and 43

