8.2.2.2. Outcome of safety evaluation

During each iSRC review, reactogenicity and safety data for approximately 140 participants (approximately 10 participants per vaccine group and placebo group stratified by age) will be monitored. The first iSRC review will occur when data collected for 7 days post dose (i.e. Day 1 to Day 7, inclusive) are available; the second review will occur based on the available data collected 7 days post dose 2 (i.e. Day 22 to Day 28, inclusive) for the same group of participants. Additional iSRC reviews may be carried out as needed.

If a safety signal is observed, GSK may decide to suspend further vaccinations in all groups or in selected groups. Guidance about how to proceed will be provided should such a decision be made.

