9.5.1.2. Final analysis (Month 13)

A final data analysis will be performed at the end of study (Month 13) of all primary and secondary endpoints based on the clean data, including evaluations of:

- Immunogenicity at all measured time points (Days 1, 22 and 43).
- Solicited administration site events and solicited systemic events data reported 7 days after each vaccination (Day 1 to Day 7 and Day 22 to Day 28).
- Unsolicited AEs and MAEs reported up 21 days after each vaccination. **(Amended 22 February 2022)**
- Concomitant medications reported up to ***21 days after each vaccination. (Amended 22 February 2022)***
- SAEs, pIMDs, and withdrawals due to AEs collected throughout the entire study.
- Pregnancies throughout the entire study.

An integrated clinical study report containing all data will be written and made available to the investigators.

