10.3.8. Recording and follow-up of AEs, SAEs, pIMDs and pregnancies

The participants will be instructed to contact the investigator immediately should the participants manifest any signs or symptoms they perceive as serious.

When an AE/SAE/pIMD/pregnancy occurs, it is the responsibility of the investigator to review all documentation (e.g. hospital progress notes, laboratory and diagnostics reports) relative to the event. The investigator will then record all relevant information regarding an AE/SAE/pIMD/pregnancy in the eCRF. The investigator is not allowed to send photocopies of the participant's medical records to GSK instead of appropriately completing the eCRF. However, there may be instances when copies of medical records for certain cases are requested by GSK. In this instance, all participant identifiers will be blinded on the copies of the medical records prior to submission to GSK.

The investigator will attempt to establish a diagnosis pertaining to the event based on signs, symptoms, and/or other clinical information. In such cases, the diagnosis should be documented as the AE/SAE and not the individual signs/symptoms.

A Paper Diary (pDiary), hereafter referred to as Participant Diary will be used in this study to capture solicited administration site or systemic events. The participant should be trained on how and when to complete each field of the Participant Diary.

At each vaccination visit, diary cards will be provided to the participant. The participant will be instructed to measure and record the oral body temperature and any solicited administration site/systemic events (i.e. on the day of vaccination and during the next 6 days) or any unsolicited AEs (i.e. on the day of vaccination and during the next 20 days occurring after vaccination). For solicited events continuing after 7 days, the participant will be instructed to record events until 21 days post-vaccination or until resolution.

Solicited events that continue after 7 days will be recorded as an unsolicited AE. The participant will be instructed to return the completed diary card to the investigator at the next study visit or by mail using the pre-stamped envelope received at the site. Details on the timing and collection of the solicited administration site and systemic events on the diary card will be described in the SPM.

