At each vaccination visit, a COVID-19 assessment card will be provided to the participant. The participant will be instructed to return the completed assessment card to the investigator at the next study visit or by mail using the pre-stamped envelope received at the site.

In addition, solicited events with a start day after day 7 post-vaccination (e.g. Day 8 after dose 1 and Day 28 after dose 2) will be recorded as unsolicited AEs.

Any individual(s) who performs the measurements of administration site or systemic events and who will enter the information into the Participant Diary should be trained on the use of the Diary. This training must be documented in the participant's source record. If any other individual, the participant is making entries in the Participant Diary, their identity should be documented in the Participant Diary/participant's source record.

- Collect and verify completed diary cards during discussion with the participant on Visit 2 and Visit 3.
- Any unreturned diary cards will be sought from the participant through telephone call(s) or any other convenient procedure.

The investigator or delegate will transcribe the required information into the eCRF in English.

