3.2 Study Endpoints

3.2.1 Primary Endpoints

Immunogenicity Endpoints

- Humoral immune response in terms of vaccine-homologous HI antibody titers:
 - Seroprotection rate (SPR) at Day 43
 - Seroconversion rate (SCR) at Day 43

Safety Endpoints

- Occurrence of AEs
 - Solicited administration site events during a 7-day follow-up period (i.e. day of vaccination and 6 subsequent days) after each vaccination
 - Solicited systemic events during a 7-day follow-up (i.e. day of vaccination and 6 subsequent days) after each vaccination
 - Unsolicited AEs and MAEs for 21 days after each vaccination
 - SAEs, pIMDs up to Day 43 visit
 - pIMDs and SAEs until Month 13

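### Protocol 10.3.8 sends a Day 28 onset after dose 2 to unsolicited AEs, and the fixed Day 22–28 wording equals the 7-day reactogenicity window only for dosing on Day 22: the passages conflict and need reconciling

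*SAP*

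**What the plan says.** The reactogenicity endpoint is defined relative to each dose. Protocol Section 3 (Table 3) has "Solicited systemic events during a 7-day follow-up (i.e. day of vaccination and 6 subsequent days) after each vaccination", and SAP 3.2.1 has "Solicited administration site events during a 7-day follow-up period (i.e. day of vaccination and 6 subsequent days) after each vaccination". The diary instruction in Protocol 10.3.8 asks participants to record "any solicited administration site/systemic events (i.e. on the day of vaccination and during the next 6 days". SAP 9.1.1 begins the same way, with reactogenicity "to be collected for 7 days following each vaccination (the day of vaccination and the following 6 days", and its next sentence then reads "Solicited events will be recorded in the eDiary for the periods Day 1 to Day 7 and Day 22 to Day 28".

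The fixed days recur elsewhere. Protocol 9.5.1.2 and SAP 10.3 attach "Day 1 to Day 7 and Day 22 to Day 28" to the solicited data of the seven days after each vaccination. Protocol 8.2.2.2 describes the data for the second iSRC review as "7 days post dose 2 (i.e. Day 22 to Day 28, inclusive"; the Figure 1 notes and SAP 3.1 repeat this.

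Study Day is counted from dose 1 (SAP 4.2). Dose 2 is allowed on Study Days 18–25 (Protocol Table 2, SAP Table 3).

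Protocol 10.3.8 also tells sites that a solicited symptom with onset after post-vaccination day 7 is unsolicited, and illustrates this with "e.g. Day 8 after dose 1 and Day 28 after dose 2) will be recorded as unsolicited AEs". Protocol 8.2.2.3, listing data that carry no formal holding rule, starts the later unsolicited period on Day 29.

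**The concern.** The Day 28 example does not fit the rule it illustrates. Its dose-1 counterpart, Day 8, is the first day outside the window. For dose 2 on the nominal Day 22, Day 28 is the last day inside. A site that follows the example would record an in-window onset as an unsolicited AE and so take it out of the primary reactogenicity endpoint.

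The category matters. Protocol 10.3.9.2 treats every solicited event as causally related, but asks for an investigator judgement on each unsolicited event. SAP 4.2 uses participants with non-missing data as the denominator for solicited events, and all vaccinated participants for unsolicited AEs. A reclassified onset therefore changes table, denominator and relatedness.

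The second issue is that Days 22–28 are stated with no indication that they are nominal, although dose 2 need not fall on Day 22. Amendment 2 added the modified per-protocol sets because out-of-window visits were more frequent than expected. Safety is analysed on the Exposed Set, which excludes nobody for dosing day. If a programmer or a data cut took the fixed days as Study Days, the dose-2 window would no longer be the one in the endpoint definition.

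**Working it through.** **Inputs.** Endpoint window: vaccination day plus 6 (Protocol Table 3, SAP 3.2.1). Fixed period: Days 22–28 (SAP 9.1.1 and 10.3, Protocol 9.5.1.2). Example: Day 28 after dose 2 (Protocol 10.3.8). Allowed dose-2 days: 18–25, read as Study Days because that is the column heading in Protocol Table 2 and SAP Table 3.

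**1. The plan's own figure.** Days 1–7: 7 − 1 + 1 = 7 days. Days 22–28: 28 − 22 + 1 = 7 days. Both agree with a 7-day window for dosing on Days 1 and 22.

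**2. The Day 28 example.** For a dose on Study Day d the window is d to d + 6, and the first day outside is d + 7.
- Dose 1: 1 + 7 = 8, as the example says.
- Dose 2 on Day 22: 22 + 7 = 29, as Protocol 8.2.2.3 has it.
- Day 28 is the first day outside only if d + 7 = 28, that is, d = 21.

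Reading the example as 28 days after dose 2 does not rescue it. That day lies outside the 21-day AE recording period in Protocol 10.3.8.1.

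**3. Effect of the example as a cut-off.** In-window days on or after Study Day 28 number max(0, (d + 6) − 28 + 1) = max(0, d − 21).

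**4. Effect of the fixed days if applied literally.** Days of the true window inside Days 22–28 number max(0, min(d + 6, 28) − max(d, 22) + 1). Days of the fixed period that precede the dose number max(0, d − 22) for d up to 29.

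| Dose-2 day d | Endpoint window | First day outside | Of 7 days, inside Days 22–28 | In-window days on or after Day 28 | Fixed-period days before dose 2 |
|---|---|---|---|---|---|
| 18 | 18–24 | 25 | 3 | 0 | 0 |
| 19 | 19–25 | 26 | 4 | 0 | 0 |
| 20 | 20–26 | 27 | 5 | 0 | 0 |
| 21 | 21–27 | 28 | 6 | 0 | 0 |
| 22 | 22–28 | 29 | 7 | 1 | 0 |
| 23 | 23–29 | 30 | 6 | 2 | 1 |
| 24 | 24–30 | 31 | 5 | 3 | 2 |
| 25 | 25–31 | 32 | 4 | 4 | 3 |

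For late doses that the modified per-protocol sets admit, the overlap is 3, 2 and 1 days for Days 26, 27 and 28, and 0 for Days 29–32.

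**5. Both together.** If Day 28 onsets also go to unsolicited, the fixed solicited period shrinks to Days 22–27. Day 22 dosing then keeps 6 days, and no dosing day keeps 7.

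**6. What the other rules use.** The endpoint, the diary instruction, the Day 43 analysis (Protocol 9.5.1.1), the SAP 9.1.1 summary categories (within 7 days of vaccination) and the SAP duration formula (days reported after the respective vaccination date) all count from the dose. The eCRF leading questions in SAP 4.5 ask about Days 1–7, and the answers are read as applying after that dose. No sentence says whether Days 22–28 are a nominal label or a programming rule.

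**The case against.** The strongest reply is that the operative rules are already relative to each dose, so the fixed days can only be the nominal schedule. Both visit-interval tables call the second visit Day 22 while allowing Days 18–25. In Protocol 8.2.2.2, Protocol 9.5.1.2 and SAP 10.3 the fixed days are a parenthesis after a phrase that counts from the dose. No Study-Day data cut is described for the iSRC, whose members have access to all available data. In Protocol 10.3.8 the rule itself, onset after post-vaccination day 7, is correct; only the illustration is wrong, by one day for nominal dosing. The same rule also prevents late onsets after an early dose 2 from being counted as solicited.

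Most of this stands. A reader might infer that only participants dosed exactly on Day 22 have a 7-day window, or that dose-2 reactogenicity will be understated. The documents support neither. Every participant has a stated 7-day window, and no passage specifies analysis by Study Days 22–28. The first inference also fails on its own terms: once the Day 28 example is applied, Day 22 dosing keeps 6 days, not 7. Nor does Amendment 2's removal of fixed day ranges for unsolicited AEs show that the remaining ranges are programming rules.

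Two things survive. No sentence labels Days 22–28 as nominal. And that label would not cure the example, which contradicts the nominal schedule itself and sits in an instruction that sites act on.

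**Conclusion.** The point holds as a conflict between passages. The Day 28 example is wrong for dosing on the nominal day. For dosing on Days 22–25, used as a cut-off, it would reclassify onsets on 1 to 4 of the 7 in-window days. This assumes that Day 28 means Study Day 28 and that sites treat it as the first unsolicited day, as Day 8 is for dose 1.

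The fixed Days 22–28 equal the endpoint window on 1 of the 8 allowed dosing days. The coverage of 3/4/5/6/7/6/5/4 of 7 days applies only under literal Study-Day use, which the plan does not prescribe.

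Neither document gives the distribution of dose-2 days or of onset days. The number of participants affected, and any effect on reported rates, therefore cannot be computed. No loss of data is established. The correction is still worth making, because it concerns a primary safety endpoint and costs almost nothing.

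**What to change.** In Protocol 10.3.8, replace the example with: *from day 8 after each dose, counting the day of vaccination as day 1 (Study Day 29 if dose 2 is given on Day 22)*.

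In SAP 9.1.1, SAP 10.3, Protocol 9.5.1.2 and the iSRC text (Protocol 8.2.2.2, SAP 3.1 and the Figure 1 notes), state the dose-2 window as the actual dose-2 date to that date plus 6, with Days 22–28 marked as nominal. While SAP 9.1.1 is open, also reconcile its eDiary with the paper diary named in the sentence before.

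The cost is wording only. The diary already runs from each vaccination, so data collection does not change. Optionally, a listing of solicited terms recorded as unsolicited with onset between the dose-2 date and that date plus 6 would show whether any site followed the example.

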9.1.2 Unsolicited Adverse Events

An unsolicited AE is an AE that was not solicited using a participant Diary and that was spontaneously communicated by the participants or a solicited administration site or systemic event that meets the criteria described in Section 0. Solicited events lasting more than 7 days after vaccination (including the day of vaccination) are also recorded as unsolicited AEs.

The original verbatim terms used by investigators to identify AEs in the Adverse Events page of the eCRF will be mapped to preferred terms (PT) using MedDRA, version to be delineated in the CSR. The AEs will then be grouped by MedDRA according to system organ class (SOC).

The following summaries will present the event count, number and percentage of participants reporting each AE and will be presented by SOC, PT, and maximum relationship to study intervention for each study group, grouped by 21 days post-vaccination at any visit and then by 2 time points (at the final analysis): 21 days post-vaccination at Visit 1, and 21 days post-vaccination at Visit 2:

- Any unsolicited AE
- Any severe unsolicited AE (grade 3)
- Any related unsolicited AE
- Any severe related unsolicited AE (grade 3 related)
- Unsolicited MAEs
- Any AEs with MAEs
- Any related AEs with MAEs

Additional summaries will present the number and percentage of participants reporting AEs in the following categories and will be presented by SOC and PT for each study group and age group from Day 1 through the Day 43 visit and from Day 1 through the end of study:

- SAEs
- AEs leading to withdrawal from study drug (through Day 22 only)
- AEs leading to withdrawal from study
- MAEs (within 21 days post each vaccination)
- pIMDs

Data listings of all AEs will be provided by participant. In addition, AEs in the categories above will be provided as listed data.

Missing data will be handled as described in Section 4.5.

